## 2.0 Change History

Version/Date	Change Log
1.0/22-JAN-2021	Created as new
2.0/01-APR-2021	
Section 9.4 Estimands – Added new tables and updated wording.
 
Section 10.5.9 Adding definition of SMQ; 6 pre-defined and 2 customized.
 
Section 10.8 Censoring rules of unblinded subjects.
 
Section 12.0 Changing to use MedDRA 24.0 instead of 23.1.
 
Section 12.8 Adding outputs occurrence of AEs related to SMQs.
 
Section 12.8.1.2 Adding of Summary of Solicited AEs by gender for dose 1, dose 2 and booster dose.
 
Section 12.8.1.2 Adding of Estimate and Credibility intervals for seroconverted subjects.
 
Section 12.9.4 Adding of Cytokine parameters
 
Appendix 6 MedDRA terms.

3.0/18-FEB-2022	
Section 8.8 and 10.8 with the protocol version 3.0 all subjects will be unblinded.
 
Section 9.1, 9.2 and 9.3 Endpoints are now described in the Estimands table (Section 9.4).
 
Section 9.4 removal of endpoint related to asymptomatic infections with SARS-CoV-2
 
Section 12.9.4 Adding of CMI analysis- data to be listed
 
Section 10.6.4 and 12.9.5 Adding of definition and Analysis of Evaluation of Asymptomatic SARS-CoV-2 infection

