On Day 29 and Day 43 
 
The proportion of subjects seroconverting for SARS-CoV-2 spike protein antibodies, as measured by ELISA.
 
Individual SARS-CoV-2 spike protein-specific antibody levels in serum, as measured by ELISA.
 
Geometric mean titers (GMTs) of serum SARS-CoV-2 spike protein antibodies, as measured by ELISA.
 
The proportion of subjects seroconverting for SARS-CoV-2 neutralizing antibodies, as measured by an activity assay.
 
Individual SARS-CoV-2 neutralizing antibody levels in serum.
 
GMTs of serum SARS-CoV-2 neutralizing antibodies, as measured by an activity assay.
 
	Immunogenicity set. Subjects receiving an authorized/licensed COVID-19 vaccine during the course of the trial will be censored at the day after intake.  Sensitivity analysis: in addition, the primary immunogenicity analysis will be repeated for subjects who received dose 1 and dose 2 (and if eligible and received a booster dose at day 57 or day 180) of trial vaccine and for whom the baseline blood sample for immunogenicity assessment was seronegative and day 43 are available for analysis and no major protocol deviations expected to impact the immunogenicity outcomes. Subjects exposed to SARS-CoV-2 prior to the trial will be excluded. Subjects will be excluded at the time point they have been exposed to SARS-CoV-2.  Estimate of subjects seroconverted (SARS-CoV-2 spike protein-specific antibodies) with 95% credibility interval using prior beta(1.9, 0.1)  Number and percentage with exact 95% confidence intervals of subjects for who a seroconversion is observed (SARS-CoV-2 spike protein-specific antibodies)  Geometric mean of Fold Change from baseline with 95% CI (SARS-CoV-2 spike protein antibodies)  Estimate of subjects seroconverted (SARS-CoV-2 neutralizing antibody levels in serum) with 95% credibility interval using prior beta(1.9, 0.1)  Number and percentage with exact 95% confidence intervals of subjects for who a seroconversion is observed (SARS-CoV-2 neutralizing antibody levels in serum)  Geometric mean of Fold Change from baseline with 95% CI (SARS-CoV-2 neutralizing antibody levels in serum)
Secondary Safety	

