
Day 57 (only for subjects receiving the booster dose on Day 57),
 
Day 85 (only for subjects receiving the booster dose on Day 57),
 
Day 180 (only for subjects receiving the booster dose on Day 57 or Day 180),
 
Day 208 (only for subjects receiving the booster dose on Day 180), and
 
Day 393 (only for subjects receiving the booster dose on Day 180):
 
 
The proportion of subjects seroconverting for SARS-CoV-2 spike protein antibodies, as measured by ELISA.
 
Individual SARS-CoV-2 spike protein-specific antibody levels in serum, as measured by ELISA.
 
GMTs of serum SARS-CoV-2 spike protein antibodies, as measured by ELISA.
 
	
Immunogenicity set. Applicable for subjects who received a booster dose at day 57 or day 180. Subjects receiving an authorized/licensed COVID-19 vaccine during the course of the trial will be censored at the day after intake.
 
Sensitivity analysis: In addition, the secondary immunogenicity endpoint will be repeated for subjects who received dose 1 and dose 2 (and if eligible and received a booster dose at day 57 or day 180) of trial vaccine and for whom the baseline blood sample for immunogenicity assessment and day 43 are available for analysis and no major protocol deviations expected to impact the immunogenicity outcomes. Subjects receiving an authorized/ licensed vaccine during the course of the trial will be censored at the day after receiving the authorized/ licensed vaccine. Subjects exposed to SARS-CoV-2 prior to the trial will be excluded. Subjects will be excluded at the time point they have been exposed to SARS-CoV-2.
 
Estimate of subjects seroconverted (SARS-CoV-2 spike protein-specific antibodies) with 95% credibility interval using prior beta(1.9, 0.1)
 
Number and percentage with exact 95% confidence intervals of subjects for who a seroconversion is

ENDPOINTS (subject level)	ESTIMANDS (population level)

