### 10.5.10 Credibility Interval and Estimate

The estimate, using  $\text{Beta}(\alpha, \beta)$ , is calculated as follows:

- $(\text{number of reactions} + \alpha) / (\text{total number of subjects} + \alpha + \beta)$ .

The lower and upper intervals are calculated as follows for a given number of reactions:

- Using SAS:  $\text{betainv}(0.025, \text{number of reactions} + \alpha, \text{total number of subjects} - \text{number of reactions} + \beta)$  and  $\text{betainv}(0.975, \text{number of reactions} + \alpha, \text{total number of subjects} - \text{number of reactions} + \beta)$ .

The SAS function `betainv` returns a quantile from the beta distribution.

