## 12.0 Statistical Methods

Due to the exploratory nature of this trial, only descriptive statistics will be used. No confirmatory statistical inference will be performed.

All data collected during this study will be displayed in data listings, unless otherwise specified. Data listings will be sorted by dose level and subject identifier. Screening failures will be excluded from all listings and tables if not otherwise stated. Listings will include all relevant assigned/derived variables.

Unless otherwise noted, categorical variables will be summarized using counts and percentages. Descriptive statistics (mean, median, standard deviation (SD), Q1, and Q3, minimum and maximum values) for continuous variable will be presented. Mean, median, Q1 and Q3 will be presented to 1 decimal more than original data. SD will be presented with 2 decimals more than original data. Minimum and maximum will match the decimal points in the original data. Maximum number of decimals will be 4, unless otherwise stated.

Expansion for subjects 18 to 60 years of age may start once the final dose for subjects in this age category has been selected based on the data from Trial CV-NCOV-001. Expansion for subjects >60 years of age may start once the final dose for these subjects has been selected based on data from this trial. Subjects enrolled in the expansion cohorts will be handled in the same manner as subjects in the first phase of the study.

The analysis will be presented in the following manner if not otherwise stated:

- Age; Overall age, age 18-60 and age >60 (61 years or older),
- Dose; any, dose 1, dose 2, booster doses at day 57 and day 180
- CVnCoV, active control (hepatitis A vaccine, or pneumococcal vaccine), and total.

Subjects in the expansion cohorts will be presented together with subjects from the initial phase of the trial.

All data summaries and tabulations will be prepared using SAS Version 9.4 or higher.

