## 12.9 Immunogenicity Analysis

### 12.9.1 Primary Immunogenicity Analyses

The primary immunogenicity will be analyzed for day 29 and 43. The primary humoral response endpoints will be analyzed with the immunogenicity set population for all available time points. All tables will be presented overall and by retrospective serology status (seropositive and seronegative) at baseline (see section 10.6.3). The primary immunogenicity endpoint will be analyzed with the immunogenicity set (see section 9.5.2). Once a subject (eligible for a booster dose) received the booster dose, the subject's measurement will be censored at the day after receiving the dose. Subjects receiving a booster dose will be analyzed separately.

The following two types of analyses will be performed:

- Estimate and 95%-credibility (using the prior beta(1.9, 0.1) intervals and proportion and 95%-confidence intervals (exact Clopper-Pearson) of subjects seroconverting with a 2-fold (definition for subjects seropositive at baseline) 4-fold increase, and any increase for subjects seronegative at baseline for SARS-CoV-2 spike (RBD) protein antibodies, as measured by ELISA, and serum SARS-CoV-2 neutralizing antibodies.

Geometric mean (GM), geometric standard deviation (GSD), 95%-confidence intervals and fold change of serum SARS-CoV-2 spike (RBD) protein antibodies, as measured by ELISA, and serum SARS-CoV-2 neutralizing antibodies.

Analysis for subjects eligible (and receiving) booster dose at day 57 or day 180 will be presented separately.

In addition, the following figures will be presented for serum SARS-CoV-2 spike (RBD) protein antibodies, as measured by ELISA, and serum SARS-CoV-2 neutralizing antibodies. All figures will be presented overall and by retrospective serology status (seropositive and seronegative) at baseline, except for subjects receiving a booster dose at day 57 or day 180 and are seropositive at baseline. For these no figures will be presented. All figures will be presented by overall age, age groups and dose level:

- Individual line plots.
- Line plots of fold change from baseline.
- Line plots of mean fold change from baseline (with 95% confidence intervals).
- Line plots of geometric mean titers (with 95% confidence intervals).
- Line plot of geometric mean fold change from baseline.

Box plot of geometric mean, minimum, Q1, median, Q3 and maximum. All immunogenicity data will be listed.

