### 12.9.2 Secondary Immunogenicity Analyses

The secondary humoral immune analyses will be repeated (based on the primary immunogenicity analyses) for subjects receiving the booster dose only for Day 57, Day 180, Day 208, and Day 393 (Months 6, 7, and 13). The secondary humoral response endpoints will be analyzed with the immunogenicity set.

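### The sizing prior Beta(1.9, 0.1) is reused for the seroconversion credibility interval with no limit to CVnCoV and no named main interval: a minor point about how results are read

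*SAP*

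**What the plan says.** Protocol 10.1 introduces Beta(1.9, 0.1) as a sizing assumption for spike seroconversion. Its mean is 1.9/(1.9 + 0.1) = 95%.

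The SAP carries the prior into the analysis. Section 12.9.1 plans "Estimate and 95%-credibility (using the prior beta(1.9, 0.1) intervals and proportion and 95%-confidence intervals (exact Clopper-Pearson) of subjects seroconverting" for both the spike ELISA and the neutralization assay. The estimands table in 9.4 lists, for spike, "Estimate of subjects seroconverted (SARS-CoV-2 spike protein-specific antibodies) with 95% credibility interval using prior beta(1.9, 0.1)" and, for neutralization, "Estimate of subjects seroconverted (SARS-CoV-2 neutralizing antibody levels in serum) with 95% credibility interval using prior beta(1.9, 0.1)". Each is followed by the data-only summary: "Number and percentage with exact 95% confidence intervals of subjects for who a seroconversion is observed". Section 10.5.10 gives the computation: "The lower and upper intervals are calculated as follows for a given number of reactions", with beta quantiles at 0.025 and 0.975.

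The booster analyses inherit the rule through 12.9.2: "The secondary humoral immune analyses will be repeated (based on the primary immunogenicity analyses) for subjects receiving the booster dose only". The change history records the addition under SAP version 2.0: "Adding of Estimate and Credibility intervals for seroconverted subjects".

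On arms, the SAP 12.0 default layout, which applies unless the SAP states otherwise, shows "CVnCoV, active control (hepatitis A vaccine, or pneumococcal vaccine), and total". Sections 9.4 and 12.9.1 state no exception for the credibility interval. Protocol 10.3.5.2, by contrast, describes seroconversion summaries by dose level.

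**The concern.** A prior with mean 95% and only 0.1 of a pseudo-non-responder expresses a belief about vaccinated subjects. Two things follow when it is used without limits.

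- **Controls.** The prior adds 1.9 pseudo-responders to a group in which few or no responders are expected. In a small control group this shifts the estimate upward and can exclude the observed value.
- **Small CVnCoV groups in which everyone responds.** The data then say little about how far below 100% the true rate may lie. The 0.1 parameter removes most of that uncertainty, so the interval is too narrow.

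The report would also carry two intervals for one primary endpoint, with nothing to say which one the text should quote. At stake is how certain the seroconversion results look, above all in the 6 µg groups and the controls. The documents treat safety differently. The Grade 3 sizing prior was Beta(0.5, 1.5), but the analysis prior is Beta(0.5, 0.5) (Protocol 10.3.5.1, SAP 12.8.2).

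**Working it through.** **Inputs.** Group sizes are from SAP Tables 1 and 2.
- 6 µg groups: 11 and 12. Booster subgroups: 30 each.
- 12 µg, initial phase: 90 per age group. Pooled with expansion: 90 + 200 = 290.
- Controls: 10 per age group in the initial phase; 10 + 20 = 30 with expansion.
- Neutralizing activity is measured only in the initial phase (Protocol Table 1). For that assay the largest dose-by-age group is therefore 90, and controls number about 10 per age group.
- All responder counts below are assumed.

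**Formulas.** From SAP 10.5.10, the estimate is (x + 1.9)/(n + 2), and the limits are the 2.5% and 97.5% quantiles of Beta(x + 1.9, n − x + 0.1). The exact limits are Clopper-Pearson. Beta(0.5, 0.5) serves only as a yardstick.

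**Reproducing the plan.** For 90/90 the estimate is 91.9/92 = 99.9%, with limits 98.9 to 100. For 72/90 it is 73.9/92 = 80.3%, with limits 71.7 to 87.7. Both match Protocol Table 6 (SAP Table 3), so the sizing figures are not in question.

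**CVnCoV groups (95% limits, %)**

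| Responders | Beta(1.9, 0.1) | Beta(0.5, 0.5) | Exact |
|---|---|---|---|
| 11/11 | 92.4–100 | 80.0–100 | 71.5–100 |
| 12/12 | 93.0–100 | 81.5–100 | 73.5–100 |
| 30/30 | 96.9–100 | 92.0–100 | 88.4–100 |
| 90/90 | 98.9–100 | 97.3–100 | 96.0–100 |
| 10/11 | 72.2–99.7 | 64.7–99.0 | 58.7–99.8 |
| 29/30 | 88.2–99.9 | 85.5–99.6 | 82.8–99.9 |
| 85/90 | 89.0–98.1 | 88.3–97.8 | 87.5–98.2 |
| 280/290 | 94.2–98.3 | 94.0–98.2 | 93.8–98.3 |

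**Coverage in the 6 µg groups.** At a true rate of 90%, all 11 respond with probability 0.9^11 = 31.4%, and all 12 with probability 0.9^12 = 28.2%. The credibility interval then starts above 90% and misses. Coverage is 67% at n = 11 and 71% at n = 12, against 98% and over 99% for the exact interval. Once the true rate exceeds the all-respond lower limit, about 92.4% (n = 11) or 93.0% (n = 12), that miss disappears and coverage is about 98% or more.

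**Coverage at n = 30 and n = 90.** Coverage was summed exactly over the binomial and averaged over 1001 equally spaced true rates from 95% to 99.5%. The credibility interval covers 86% at n = 30 and 88% at n = 90.

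**Controls with no responders**

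| Count | Beta(1.9, 0.1) estimate | 95% limits | Exact |
|---|---|---|---|
| 0/10 | 1.9/12 = 15.8% | 2.0–40.1 | 0% (0–30.8) |
| 0/30 | 1.9/32 = 5.9% | 0.7–16.2 | 0% (0–11.6) |

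**Total column.** Take neutralization in subjects over 60, with 12 + 90 CVnCoV subjects all responding and 10 controls with none. Then 102/112 gives 85.3 to 95.6, against 84.2 to 95.6 exact. The numeric effect is small, but a 95% prior mean does not describe such a mixture.

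**The case against.** The strongest reply is that little is missing. The exact interval is already planned for both assays, the prior and formula are printed, and the SAP's own Table 3 openly shows 98.9 to 100 for 90/90. The analysis is descriptive and no decision rule uses the credibility interval. Two clearly named summaries can stand side by side. This all stands, and it makes the point minor. It does not make a control estimate of 15.8% meaningful when nobody responded.

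A second reply is that the 21-point gap at 11/11 (92.4 against 71.5) overstates the fault, because the exact interval is conservative: its mean coverage at n = 11 is 98.9% over true rates of 85 to 99.5%. This also stands. Against Beta(0.5, 0.5) the gap is 92.4 − 80.0 = 12.4 points, and the remaining 80.0 − 71.5 = 8.5 points reflect the choice of yardstick. Frequentist coverage is likewise a reviewer's criterion; the SAP does not promise it.

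A third reply is that nothing says outright that controls will get this prior, and Protocol 10.3.5.2 speaks of dose levels. That is fair: use in controls follows from the SAP default layout, not from an explicit statement.

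A reader might also infer that the prior was brought in without authority. The documents do not support this. Protocol 10.3.1 leaves further analysis methods to the SAP, and the addition is logged.

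**Conclusion.** The point holds as a minor one about specification and reading. Beta(1.9, 0.1) is carried from sizing into the analysis of both assays with no arm limit and no main interval. Under the default layout it would give controls without responders an estimate and interval that exclude the observed 0%. It would also give all-respond CVnCoV groups an interval that is too narrow. Both results rest on assumed responder counts.

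A reader might infer that the 6 µg intervals are too narrow whatever the true rate. They are not. Undercoverage there needs a true rate below about 92.4% (n = 11) or 93.0% (n = 12), and at the design target of above 95% those groups are covered about 98% of the time or more. At that target the shortfall lies at n = 30 and n = 90. The n = 30 booster groups bear only on the secondary endpoint. With several non-responders or at n = 290 the choice of interval hardly matters.

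A reader might also infer that a dose or trial decision is at risk. Neither document ties an analysis-stage decision to this interval.

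**What to change.** Amend SAP 9.4 and 12.9.1; 12.9.2 follows by reference.

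1. State that the observed proportion with the exact Clopper-Pearson interval, already planned, is the main seroconversion result in every arm.
2. Label the Beta(1.9, 0.1) estimate and interval as supportive and present them for CVnCoV groups only. Do not compute them for active control or for the total column.
3. Record the change in the SAP history with its date, as made after the three interim analyses reported in SAP 11.1.

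The prior itself stays as specified and still matches Protocol Table 6 and SAP Table 3. No new computation is needed.

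The cost is a wider main interval (lower limit 71.5 instead of 92.4 at 11/11, and 96.0 instead of 98.9 at 90/90) that is also conservative. Its mean coverage is about 96 to 99% over true rates of 85 to 99.5% for the group sizes above. The choice is also made late, with an unblinded sponsor (SAP 8.7), which is why it must be dated. When all CVnCoV subjects respond it selects the less favourable of the two planned intervals, which limits any suspicion that it was chosen to suit the data.

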### 12.9.2 Secondary Immunogenicity Analyses

The secondary humoral immune analyses will be repeated (based on the primary immunogenicity analyses) for subjects receiving the booster dose only for Day 57, Day 180, Day 208, and Day 393 (Months 6, 7, and 13). The secondary humoral response endpoints will be analyzed with the immunogenicity set.

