### 10.1 Baseline and Change from Baseline

Unless otherwise noted, baseline is defined as the last valid measurement at Visit 1: Day 1 prior to administration of the trial vaccine.

---

Change from Baseline is defined as:

Observed result at nominal time point – observed result at baseline.

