## 10.2 Fold change from Baseline

Unless otherwise noted, fold change from baseline is defined as the ratio:

Post-baseline value/baseline value.

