#### 10.6.2.1 SARS-CoV-2 RBD of S Protein Antibodies

In subjects who tested seronegative to the N protein for SARS-CoV-2 at baseline (see Section 10.6.3), seroconversion is defined as a fold increase above 1 in antibody titer against SARS-CoV-2 RBD of S protein.

In subjects who tested seropositive to the N protein for SARS-CoV-2 at baseline (see Section 10.6.3), the definition for seroconversion is a fold increase above 2 in antibody titer against SARS-CoV-2 RBD of S protein versus baseline.

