### 12.9.3 Sensitivity Immunogenicity Analyses

A sensitivity analysis will be performed for the primary and secondary humoral immune response endpoints.

Applicable for sensitivity analysis for 1) 2-dose regime and 2) in addition for subjects eligible for a booster dose and receiving booster dose at day 57 or day 180. As per the immunogenicity set in section 9.5.2 with the additions:

- Subjects receiving dose 1 and dose 2 (for the separate booster sensitivity dose analysis the subjects must have received the booster dose at day 57 or day 180).
- Subjects must have no protocol deviation with impact on the immunogenicity measurement.
- Subjects in the 2-dose regime: The baseline blood sample for immunogenicity assessment and one sample at least 14 days after receiving the second dose.
- Subjects eligible and receiving a booster dose: The baseline blood sample for immunogenicity assessment and one sample at least 14 days after receiving the booster dose are available for analysis.
- Subjects must not be exposed to SARS-CoV-2 before the trial or during the trial before the endpoint evaluation.

---

For the tables the N will however be based on the immunogenicity set as per definition in section 9.5.2. The seroconversion rates are based on the n at relevant time point.

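### The booster analysis measures seroconversion and fold change from Day 1, plans no paired pre- to post-booster ratio, and drops Day 85 from its visit list

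*SAP*

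**What the plan says.** The secondary objective (protocol 4.1.2, SAP 7.2) is the humoral response after a booster dose. SAP 12.9.2 carries it out by repetition: "The secondary humoral immune analyses will be repeated (based on the primary immunogenicity analyses) for subjects receiving the booster dose". The reference point therefore comes from the general definitions.

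- SAP 10.1: "Unless otherwise noted, baseline is defined as the last valid measurement at Visit 1: Day 1 prior to administration of the trial vaccine".
- SAP 10.2: "Unless otherwise noted, fold change from baseline is defined as the ratio" of the post-baseline value to the baseline value.
- SAP 10.6.2.1, for subjects N-seronegative at baseline: "seroconversion is defined as a fold increase above 1 in antibody titer against SARS-CoV-2 RBD of S protein". A rise above 2-fold is required if N-seropositive. SAP 10.6.2.2 uses the same thresholds for neutralizing antibodies.

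The booster rows of SAP 9.4 again use seroconversion and fold change from baseline. SAP 12.9.1 also plans geometric means with intervals, listings and figures, including "Line plots of geometric mean titers (with 95% confidence intervals". Protocol Table 1, footnote t, requires the Day 57 and Day 180 samples to be drawn before vaccination.

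On visits, SAP 12.9.2 reads "for subjects receiving the booster dose only for Day 57, Day 180, Day 208, and Day 393 (Months 6, 7, and 13". SAP 9.4 lists, in addition, "Day 85 (only for subjects receiving the booster dose on Day 57", as does protocol 4.2.2.

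**The concern.** A subject who reaches the booster visit has already had two doses. Any rise over Day 1 that is still present then counts towards seroconversion and fold change after the booster. A booster that did nothing would still show whatever seroconversion and fold rise persisted from the primary series.

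At Day 85 and Day 208 only boosted subjects are sampled, so those visits have no concurrent unboosted group. The subject's own pre-booster sample is the natural reference. It is collected, but the SAP never uses it as one. A reader would have to infer the booster change from two separate GMTs, without an interval that uses the within-subject pairing.

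The Day 85 omission is a different kind of problem. Day 85 is the 28-day post-booster visit for the Day 57 booster subgroup. If 12.9.2 is programmed as written, the main booster analysis loses that sample.

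**Working it through.** **Reference point.** SAP 10.1 allows exceptions where noted. None appears in SAP 9.4 (secondary immunogenicity), 10.6.2, 12.9.1 or 12.9.2. SAP 12.9.1 presents booster recipients separately but does not change the reference. Protocol Table 1 calls the pre-dose Day 57 and Day 180 samples baseline samples, but the SAP does not adopt that. Day 1 therefore applies to the booster.

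**What a Day 1 reference shows.** Assume a titer 10-fold above Day 1 just before the booster. If the booster halves, leaves unchanged or doubles the titer, the Day 1 fold change is 5, 10 or 20. An N-seronegative subject counts as seroconverted in all three cases. If all 30 of a subgroup are in that position, SAP 10.5.10 with the Beta(1.9, 0.1) prior gives (30 + 1.9)/(30 + 2) = 99.7% (95% credibility interval 96.9 to 100) whatever the booster did.

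**How much headroom is left.** The plan states no figure for this point, so I use the scenario rates in protocol Tables 6 and 7 as illustration. Those tables reproduce: Table 6 to within 0.1 point, Table 7 to within 2 points, and the worked example (n=200, adverse reaction rate 20%, seroconversion 97.5%) at 76%. They are spike-antibody design scenarios, not observed rates, and not rates for neutralizing antibodies or for persistence to Day 180. Protocol Table 2 gives three booster subgroups of 30, or 60 on the Day 180 schedule pooled over age. With pre-booster rate p, the expected number unconverted is n(1 − p) and the chance that all are already converted is p^n.

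| p | n=30: unconverted | n=30: all converted | n=60: unconverted | n=60: all converted |
|---|---|---|---|---|
| 90% | 3.0 | 4.2% | 6.0 | 0.2% |
| 95% | 1.5 | 21% | 3.0 | 4.6% |
| 97.5% | 0.75 | 47% | 1.5 | 21.9% |

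Lower pre-booster rates or waning leave more headroom.

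**What pairing is worth.** The documents give no titer SD or within-subject correlation, so I assume a log10 SD s of 0.4 to 0.6 and a correlation r of 0.5 to 0.8. The 95% limits of the post/pre ratio are the estimate multiplied and divided by:

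- independent GMTs: 10^[t(0.975, 2n − 2) · s · √(2/n)]
- paired: 10^[t(0.975, n − 1) · s · √(2(1 − r)/n)]

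| n | s | Independent | Paired, r=0.5 | Paired, r=0.8 |
|---|---|---|---|---|
| 30 | 0.4 | 1.61 | 1.41 | 1.24 |
| 30 | 0.5 | 1.81 | 1.54 | 1.31 |
| 30 | 0.6 | 2.04 | 1.68 | 1.39 |
| 60 | 0.4 | 1.40 | 1.27 | 1.16 |
| 60 | 0.5 | 1.52 | 1.35 | 1.21 |
| 60 | 0.6 | 1.65 | 1.43 | 1.25 |

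**Day 85.** SAP 9.4, protocol 4.2.2 and protocol Table 1 include it. SAP 12.9.2 does not, and SAP 6.1 records no such change from the protocol. Day 85 − Day 57 = 28 days, and Day 180 − Day 57 = 123 days. Without Day 85, the Day 57 booster subgroup has one post-booster visit, Day 180. The Day 180 boosters keep their 28-day visit (208 − 180 = 28). The sensitivity analysis does not close the gap: SAP 12.9.3 asks only that "one sample at least 14 days after receiving the booster dose are available for analysis", which a Day 180 sample alone would satisfy. The months named in 12.9.2 match only Days 180, 208 and 393, so the list may predate the Day 57 booster; that is an inference.

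**The case against.** The strongest reply is that little is hidden. Days 57 and 180 are themselves analysis visits with pre-dose samples, so seroconversion, GMT and fold change are reported for boosted subjects before the dose as well as after it. A booster without effect would show similar values at Day 180 and Day 208. Individual levels and GMTs are not tied to Day 1 at all. With the same subjects at both visits, the ratio of the two GMTs equals the geometric mean of the within-subject ratios. SAP 12.9.1 also plans 2-fold and 4-fold rises, which saturate less easily than any rise. The Day 1 reference for seroconversion follows protocol 9.2.1, the trial is descriptive, and SAP 9.2 makes section 9.4 the source of the endpoints, so Day 85 looks like a clerical slip. Ratios added now would also follow the Day 208 booster interim (SAP 11.1), to data for which SAP 8.7 has the sponsor unblinded.

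Much of this stands. No booster data are lost, a point ratio can be formed, the SAP does not itself plan the independent interval used above for comparison, and Day 85 is an inconsistency rather than a removed endpoint. It does not supply what is missing: a specified paired interval and a response defined from the pre-booster value. The 4-fold summary is still measured from Day 1. Nor does the reference in SAP 12.9.1 to all available time points settle Day 85, because it concerns the primary endpoints and that section censors subjects the day after the booster.

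**Conclusion.** Both parts hold and should be fixed. The text establishes that the booster endpoints of seroconversion and fold change use Day 1, that no paired pre- to post-booster ratio is specified although the samples are scheduled, and that 12.9.2 disagrees with SAP 9.4 and the protocol on Day 85. The consequence is limited: the secondary booster objective is answered less directly than the data allow, and one 28-day visit in a subgroup of 30 is at risk if 12.9.2 is followed literally. The headroom figures rest on design-scenario rates and the interval widths on assumed SDs and correlations. They show the kind of gain available, not a magnitude established for this trial.

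**What to change.** 1. Add Day 85 to the visit list in SAP 12.9.2, to match SAP 9.4 and protocol 4.2.2.
2. In SAP 10.1 and 12.9.2, define an additional pre-booster baseline: the last valid sample before the booster dose. For both assays, report the within-subject geometric mean ratios Day 85/Day 57 (Day 57 booster) and Day 208/Day 180 (Day 180 booster) with paired 95% confidence intervals, plus the proportions with 2-fold and 4-fold rises from the pre-booster value. Present them by age group and, for the Day 180 schedule, also pooled.
3. Keep the protocol-defined Day 1 seroconversion and fold-change endpoints as they are.
4. Record in the change log and SAP 6.1 that the ratios were added after the Day 208 booster interim, and state that they are an uncontrolled before/after comparison.

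The cost is SAP wording, one derived baseline and a few table columns. All samples are already scheduled; no subject or visit is added and no protocol endpoint changes.
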